10.1 Data Confidentiality

- We will take extensive measures to ensure data safety and security. A dedicated study database will be constructed on a secure server using the REDCap study management system.⁵⁶ To ensure quality control and appropriate completion of self-report measures, questionnaires will be collected online. Data quality will be checked by examining descriptive statistics and checking ranges of missing values.

10.1.1 Confidentiality of Subject Records

By signing the protocol, the Investigator agrees that *IRB and NCI* representative may consult and/or copy study documents in order to verify CRF data. By signing the consent form, the subject agrees to this process. If study documents will be photocopied during the process of verifying CRF information, the subject will be identified by unique code only and full names and similar identifying information (such as medical record number or social security number) will be masked.

The Clinical Site Investigators will ensure that the identity of subjects will be protected. All study records will be maintained in a secure fashion with access limited to essential study personnel only. All study documents submitted to the Coordinating Center will have identifiers removed other than dates of birth and service and subjects will be identified with a study-specific identification number only. The Clinical Site Investigators will maintain, in a secure location, an enrollment log that includes subject identifying information and links subjects to their study-specific identification number.

10.2 Data Capture

10.2.1 Missing Data

Strategies for handling missing data will be chosen based on the type and extent of the problem under advisement from biostatistician [name]. It is anticipated that sensitivity analyses or model-based approaches will be assessed for appropriateness for this investigation.

10.2.2 Data Collection Tools

UW-ICTR provides REDCap that will be used for data collection for this investigation. This tool is self-service, secure, and can be easily used across all study sites to ensure appropriate data collection. Additionally, this tool is buildable for the unique needs of this investigation, and we plan to use the participant as the unit of measure for this study, and not the time point as the unit of measure.

10.3 Records Retention

To ensure the integrity of the data collected from study participants, several procedures will be implemented. All personnel involved in data collection will be thoroughly trained in all assessment methods, thus ensuring consistent applications of procedures and measurement consistency across participants. All questionnaire data will be automatically saved in the secured, password protected Qualtrics or REDCap systems and will be downloaded to a password protected network folder on a secure server (i.e., password protected) which is backed up daily ensuring access only by the investigators. All other data will be saved to a computer hard drive in real time and then stored on a secure server (i.e., password protected) which is backed up daily. All raw data are kept in locked cabinets in the site-PI's laboratory. All hardcopies of raw data will be de-identified (with the exception of the study ID number) and copied for mailing to the coordinating center for data management. Although all packages with data will be mailed by certified mail so that tracking the location is possible, maintaining copies of the data at the collaborating centers in locked cabinets in the site investigator's laboratory will be done in the unlikely event that data is lost in the mail. Informed consent forms will be kept in a separate locked file cabinet with restricted access. Issues related to data integrity will be discussed on a weekly basis as a recurring agenda item in the weekly project meeting. Finally, continuing review of all procedures will be obtained by all appropriate institutional review boards.

Study data will be labeled with a study ID number. Data linking the study ID numbers with subject identities will be stored in hard copy format only. This and other paper files will be kept in a locked file cabinet in the Physical Activity Laboratory in the UW Department of Kinesiology ([name]). The laboratory door is kept locked at all times. Only study personnel will have access to participant data. Electronic data, including accelerometer data files, will be kept on a server at the Department of Kinesiology, in a drive accessible only by the PI and study staff. Data will be retained for an indefinite amount of time, and all study data will be banked in a coded format. Data may be used in the future for a secondary data analysis looking at relationships between collected study data and other variables. Study data may only be used by the study team, and all future investigations using any banked data from this study must undergo a separate IRB application. Use of study data is limited to the research team for this protocol, unless a separate IRB application is submitted for use of this banked data for future investigations.

10.4 Data and Safety Monitoring

The Site Investigator ([name]) will be responsible for reviewing and monitoring all study data and any adverse events for this study. The Investigator will meet with study personnel at least weekly to evaluate study progress, including periodic assessment of data quality and timeliness, participant recruitment, accrual and retention, participant risk versus benefit, and other factors that can affect study outcomes. All unanticipated problems regardless of where they occur, will be reported to the University of Wisconsin IRB.

This protocol is considered to have a minimal risk to participants, as it prescribes physical activity that is consistent with national recommendations and guidelines for cancer survivors. We attempt to reduce the risk of injury or muscular soreness by excluding individuals who report difficulty transitioning from sitting to standing, walking 1 block (as a proxy measure of basic physical functioning), or report that they are otherwise unable to work towards the intervention goals. As with any exercise intervention, there is also a minor risk of cardiovascular events. Participants in both intervention groups will receive regular check-in calls to assess progress and address any potential problems regarding physical issues or emotional stress.

11 Assessment of Safety

This protocol is considered to have a minimal risk to participants, as it prescribes physical activity that is consistent with national recommendations and guidelines for cancer survivors. We attempt to reduce the risk of injury or muscular soreness by excluding individuals who report difficulty transitioning from sitting to standing, walking 1 block (as a proxy measure of basic physical functioning), or report that they are otherwise unable to work towards the intervention goals. As with any exercise intervention, there is also a minor risk of cardiovascular events. Participants in both intervention groups will receive regular check-in calls to assess progress and address any potential problems regarding physical issues or emotional stress.

12 Study Finances

12.30 Funding Source

This study is financed through an institutional pilot grant from the American Cancer Society and funds from the UWCCC.

12.31 Conflict of Interest

Any investigator who has a conflict of interest with this study (patent ownership, royalties, or financial gain greater than the minimum allowable by their institution, etc.) must have the conflict reviewed by a properly constituted Conflict of Interest Committee with a Committee-sanctioned conflict management plan that has been reviewed and approved by the study sponsor prior to participation in this study. All UW investigators will follow the UW conflict of interest policy.

12.32 Subject Stipends or Payments

Participants will be paid \$50 in cash at the baseline visit as well as another \$50 cash at the final (post-intervention) visit. Those who complete the intervention will receive a total of \$100 cash.

13 Publication Plan

The primary responsibility for publication of the results of this study are the investigators at UW Madison ([name]). Neither the complete nor any part of the results of the study carried out under this protocol, nor any of the information provided by the sponsor for the purposes of performing the study, will be published or passed on to any third party without the consent of the study sponsor. Any investigator involved with this study is obligated to provide the sponsor with complete test results and all data derived from the study.

14 Protocol implementation timeline and contingency plans

There are three primary concerns for this research design and there are listed preliminary contingency plans if these concerns come to fruition:

- The primary concern is a lack of subjects or low accrual to study participant goals for site numbers.
 - If there is insufficient or slow recruitment through a clinical route, we plan to reach out to community support groups such as Gilda's Club to bolster recruitment numbers. This strategy will not replace the clinical route, but may increase participant enrollment.
- The secondary concern is high attrition in the treatment group and potential losses to follow up over the course of the 10-week intervention. Although this is a lower probability event, we will utilize the following contingency plans:
 - Deploy follow ups using a support person for the participant that we can contact if the participant is not contacting study staff or seems to be lost to follow up
 - At the start of the study, we will collect multiple email addresses and phone numbers from

each participant to avoid this problem *a priori*.

- Finally, we may have poor adherence and compliance to the protocol.
 - We have pre-scheduled check-ins during the course of the intervention to avoid this issue
 - However, we will deploy additional health coaching if necessary where participants are really struggling with adherence
 - Participant satisfaction surveys will be used at the end of the intervention to evaluate the quality of the study to learn and improve for the future if adherence is very high

Table 5: Protocol implementation timeline for the home-based resistance training protocol in endometrial cancer survivors

	Pre-award	Year 1	Year 2
Protocol development			
PRMC/IRB Approval			
Recruitment			
Data collection			
Data analysis			
Manuscript preparation			
Data closeout protocols			
Manuscript publication			

Appendix 1: Participant tracking form: Checklist of Study Activities

Activity	Date completed	Staff initials
Screening call	/ /	_____
Baseline Assessments (all participants)		
Confirmation Letter sent	/ /	_____
Demographics and cancer characteristics	/ /	_____
Physical Measures (FFT and Anthropometrics)	/ /	_____
DXA Scan	/ /	_____
Blood biomarkers collected	/ /	_____
Questionnaire links emailed (5 questionnaires)	/ /	_____
Actigraph/instructions given	/ /	_____
Randomized to:  Intervention  Wait-list	/ /	_____
If intervention: Instructional visit scheduled	/ /	_____
Baseline Questionnaires verified	/ /	_____
Baseline incentive provided	/ /	_____
Instructional Visit (Intervention group)		
Date of visit – all exercises taught	/ /	_____
Participant exercise materials delivered	/ /	_____
ActiGraph data downloaded/checked	/ /	_____
Intervention materials provided (Both groups)	/ /	_____
Intervention Period (Intervention group)		
Date of first coaching call (1A)	/ /	_____
Date of second coaching call (1B)	/ /	_____
Date of week 2 coaching call (2)	/ /	_____
Date of week 3 coaching call (3)	/ /	_____
Date of week 4 coaching call (4)	/ /	_____
Actigraph mailed out	/ /	_____
Mid-point (5 week) Questionnaires Sent (5)	/ /	_____
Mid-point Questionnaires Verified	/ /	_____
Date of week 6 coaching call (6)	/ /	_____
Date of week 8 coaching call (8)	/ /	_____
Actigraph data downloaded/checked	/ /	_____

Final Assessments (all participants)

Final visit scheduled	/	/	
ActiGraph mailed	/	/	
Questionnaire links emailed (5 questionnaires)	/	/	
Questionnaires verified	/	/	
Physical Measures (FFT and Anthropometrics)	/	/	
DXA Scan	/	/	
Blood biomarkers collected	/	/	
Accelerometer downloaded/checked	/	/	
Incentive delivered	/	/	
Qualitative interview with study coordinator	/	/	

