7.7.2 Data Collection and Follow-up for Withdrawn Subjects

Data will be attempted to be gathered from participants who have withdrawn from the study to collect their data prior to their withdrawal, including emails from the research staff and telephone calls.

Withdrawn subjects will be analyzed using an intent to treat analysis, therefore maximizing the amount of data is paramount to success. However, if participants cannot be contacted after 3 attempts from the study team (both telephone calls and emails) then the participants will be considered lost to follow-up.

8 Study Procedures

Wait list interventions

After being randomized to the wait-list group, participants will be scheduled for their 10 week follow up visit. The wait list arm will not have the additional five week follow up that the exercise arm receives. Participants will be reminded that at that final visit, participants will complete the same study measures (body composition, functional fitness testing, blood sample collection, and anthropometrics) and will also receive study materials at the end of their wait list period. Participants in the wait list group will also complete accelerometer (Actigraph) assessments at three study points: Early in the intervention near the instructional visit, at the mid-way (5-week) mark, and before the final visit. These accelerometers will be sent and received via mail and participants will receive instructions on how to wear, use and send to us during the instructional visit.

Exercise interventions

After being randomized to the exercise (intervention) arm, participants will be scheduled for an instructional visit with the study coordinator within a week of randomization. At that visit, participants will be instructed to wear comfortable clothes and shoes for learning the exercises. The instructional visit includes going through each exercise of the intervention (see Table below) to learn the movement, learn the muscle groups involved, and to learn how to monitor themselves by tracking their progress via logs. This instructional visit should take 60-90 minutes, and each participant will receive a summary sheet of her starting point at each exercise with respect to intensity and progressions/regressions. For example, a participant may be starting on a blue resistance band for biceps curls, but the squats may simply be body weight at this time. Table below outlines the exercises for the intervention.

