8.5 Study Visits

8.4.1 Screening/Baseline:

Baseline. At this visit, the study coordinator will explain the study and obtain written informed consent. Physical measurements (anthropometrics, blood sample, DXA scan, functional fitness testing) will be completed. The study coordinator will instruct the participant on how to properly wear the accelerometer (to be returned via pre-paid mailer), complete a 7-day PA log, and complete the online questionnaires.

Randomization. After all baseline measures have been completed and checked, the participant will be randomized with 1:1 probability to the intervention or wait-list control group. A blocked randomization scheme will ensure equal allocation of participants to each group. Participants will be notified of their group assignment by phone; those in the intervention group

Table 4. Acceptable Window for Study Visits (including weekends)

Visit	Window	Activities
Randomization	+/- 5 days	Allocate to group
Instructional visit	+/- 2 weeks	Teach exercises, learn how to interface with software, how to log exercises
Final visit	+ /- 2 weeks	Collect final measures

8.4.3 Unscheduled:

- Pain or concerns that need to be addressed in person
- Adverse event follow ups with PCP

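### The Appendix 1 form and the Table 4 window do not enforce the Section 8.4.1 rule that baseline is complete before randomisation, so some self-report baselines could follow disclosure of the arm

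*Combined protocol and SAP*

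**What the plan says.** The governing text is in Section 8.4.1, printed under 8.5 Study Visits: "After all baseline measures have been completed and checked, the participant will be randomized with 1:1 probability". The woman is then told her arm: "Participants will be notified of their group assignment by phone".

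Some of the baseline measures cannot be finished at the visit. There the coordinator instructs the participant to wear the accelerometer ("to be returned via pre-paid mailer") and to "complete a 7-day PA log, and complete the online questionnaires".

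Table 4, in the same section, gives randomisation a window of plus or minus 5 days and does not say which day it is counted from.

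The tracking form in Appendix 1 lists, in this order:

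1. "Questionnaire links emailed (5 questionnaires"
2. ActiGraph handed over
3. Randomisation
4. Scheduling of the instructional visit (intervention arm only)
5. "Baseline Questionnaires verified"
6. Baseline incentive

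The row "ActiGraph data downloaded/checked" comes later still, in the instructional-visit block. Section 8 places that visit after allocation: "participants will be scheduled for an instructional visit with the study coordinator within a week of randomization". The form has no row for the 7-day activity log.

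**The concern.** Section 8.4.1 makes a checked baseline a condition of randomisation. The form that records these steps places the questionnaire check after randomisation, and it has no row showing when a woman actually answered. The timing window gives staff no fixed point that would restore the order.

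The trial is open, and the measures at risk depend on expectation: self-efficacy for strength training, FACT-En quality of life, PROMIS mental well-being and self-reported activity. A woman who has just learned that she will train, or that she must wait, may answer differently from one who does not know. A baseline given in that state alters both the pre-post change and the between-arm difference. Section 9.3.1 plans to estimate both, and to use longitudinal analyses to gauge the size of change to be expected. If it happened, the form as printed would not show which records were affected.

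**Working it through.** No planned figure bears on this point. Section 9.1 sets the sample of 40 on feasibility grounds, with no effect size. The check is therefore a comparison of sequences and a day count.

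**Sequence**

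| Step | Section 8.4.1 | Appendix 1 row order |
|---|---|---|
| Questionnaires | Completed and checked before randomisation | Links sent before randomisation; verification listed after it |
| 7-day activity log | A baseline measure, so before randomisation | No row |
| Accelerometer | A baseline measure, so before randomisation | Handed over before randomisation; data check under the later instructional visit |

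The form's order carries some weight. It runs from screening through baseline, randomisation, instructional visit, coaching calls and mid-point to the final visit. In the mid-point and final blocks, sending the questionnaires is followed directly by verifying them. Only in the baseline block do randomisation rows come between the two.

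For the accelerometer, Section 8 also places the first assessment close to the instructional visit, although Section 8.1 calls it baseline.

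**Day count for Table 4**

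Inputs: a window of plus or minus 5 days (Table 4) and a log of 7 days begun at or just after the baseline visit (Section 8.4.1). Call the baseline visit day 0. The log ends on day 6 if the visit day is its first day, or on day 7 if it starts the next day.

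| Window counted from | Window | Log ends | Result |
|---|---|---|---|
| Baseline visit, log starts that day | day −5 to +5 | day 6 | closes 6 − 5 = 1 day too early |
| Baseline visit, log starts next day | day −5 to +5 | day 7 | closes 7 − 5 = 2 days too early |
| Baseline completion on day 6 | 6 − 5 = day 1 to 6 + 5 = day 11 | day 6 | days 1 to 5 precede completion |
| Baseline completion on day 7 | 7 − 5 = day 2 to 7 + 5 = day 12 | day 7 | days 2 to 6 precede completion |
| A planned randomisation date | not determinable | – | – |

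Postal return of the accelerometer adds further days. The first two rows also have a minus side that falls before the visit at which consent is obtained.

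**Size of any bias**

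Suppose a fraction f of women in each arm answer after learning their allocation, and that this knowledge moves the between-arm baseline difference among them by d standard deviations. The baseline difference is then biased by f × d, and the between-arm difference in change scores by −f × d. The documents give neither f nor d, so no figure follows.

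**The case against.** The strongest reply is that the protocol already states the right rule. Section 8.4.1 forbids randomisation before baseline is complete, and the phone call comes only after that, so a post-allocation baseline would need staff to depart from the text. This stands. A reader might infer that the plan permits or intends baselines after allocation; the documents do not support that.

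The form is also imperfect evidence of timing. Each row has its own date, and nothing says the rows are chronological. The baseline incentive sits below randomisation although Section 7.6.6 pays it at the baseline visit. A row for intervention materials covering both groups sits under the instructional visit, although Section 8 has wait-list women receive materials at the end of their wait. Verification is a staff check and does not show when the woman answered; the links go out before randomisation. All of this weakens the inference that answers come late. It does not remove the mismatch with a rule that requires checking as well as completion.

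On Table 4, a reader might infer that no site can satisfy both the window and Section 8.4.1, or that every woman falls short. That holds only if the window is counted from the baseline visit. Counted from completion of baseline, randomising on days 0 to +5 meets both. What remains is that the reference day is missing and that, on either of these anchors, the minus side admits randomisation before baseline is complete.

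Finally, the measures exposed are secondary self-reports in a feasibility pilot with a descriptive aim. That limits the consequence, although Section 9.3.1 does plan to estimate change from them.

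**Conclusion.** The point holds as a conflict between the governing text and two operational items. Appendix 1 places the questionnaire and ActiGraph checks after randomisation and does not track the 7-day log. Table 4 has an unanchored two-sided window that fits Section 8.4.1 only in part. The conflict in row order and the missing reference day can be read directly from the documents.

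The consequence is less certain. It depends on staff following the form or the window rather than Section 8.4.1, on some women answering after the phone call, and on that knowledge changing their answers. The shortfall of 1 to 2 days assumes that the window is counted from the baseline visit. The size of any bias cannot be quantified from the documents. It would affect the secondary pre-post and between-arm estimates for self-efficacy, quality of life, PROMIS measures and self-reported activity. Primary adherence has no baseline value and is unaffected. The correction should be made, but the point does not threaten the trial's main aim.

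**What to change.** In Appendix 1, move questionnaire verification above the randomisation row and add a row there for receipt of the 7-day log. Record the date on which the woman completed each, as well as the date staff checked it. Require these rows to be filled before the allocation is released. Settle the baseline ActiGraph check in the same edit: as Section 8.4.1 is worded, it too belongs before randomisation.

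In Table 4, replace the plus or minus 5 days with 0 to +5 days, counted from the date on which all baseline measures are verified complete.

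The cost is a reordered form with an added row and one changed line in a table. Randomisation will be delayed a little for women who are slow to return questionnaires or logs, and a few may be lost before they are randomised.

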or demonstrate issues with exercises or their form. At the mid-point of the study, participants will receive an email with the questionnaires, so that the questionnaires will be done at baseline, at the study mid-point, and at the final visit.

Participants in the intervention group will also complete accelerometer (Actigraph) assessments at three study points: Early in the intervention near the instructional visit, at the mid-way (5-week) mark, and before the final visit. These accelerometers will be sent and received via mail and participants will receive instructions on how to wear, use and send to us during the instructional visit.

At the end of the 10 week period, participants will return to the UW campus for a final visit to repeat baseline study measures. At this time, intervention arm participants will also complete an exit-style interview with the study coordinator to help improve the intervention for future participants. This will be recorded, but anonymized upon transcription.

While the formal intervention period will be 10 weeks in duration, we will continue to follow those in the exercise arm for five weeks post-final assessment. This follow up period will consist of surveys to the participants assessing the frequency of the home-based resistance exercise, to determine if the behavior of exercise persists in the short-term following intervention conclusion.

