- Functional fitness. The functional fitness test (FFT) is a battery of six tests measuring strength, flexibility, fitness, body composition, and agility. It has high test-retest reliability and is suitable for tracking within-person changes.³¹ The functional fitness test battery includes the following 6 assessments: 1.) **The 30 second chair stand**, which assesses the strength of the lower body. Each person will have 30 seconds to stand up and sit down from a chair as many times as possible within the time frame. 2.) **The 30 second arm curl** assesses the strength of the upper body, where women will hold a 5 pound dumbbell in a seated position, and they will have 30

seconds to curl their arm and extend it as many times as possible within the time frame. 3.) The **6 minute walk test** measures the total distance that a person can quickly walk on a flat hard surface within a period of 6 minutes, using a 100ft length of distance. 4.) **The chair sit and reach** assesses the lower body flexibility where the participant will sit in a chair, extend one leg in front of them and flex at the waist, reaching toward their toes, and we will measure the distance between their toes and fingers. 5.) **The 8-foot-up and go** is an assessment of speed agility and balance. With this assessment, the participant begins in a seated position, and will be timed for the duration it takes to rise from the chair, walk as quickly as possible around a cone 8 feet away from the chair, and return to a seated position. 6.) **The back scratch test** is an assessment of the flexibility of the upper body, where the person will be seated and one arm will be flexed behind the head, and the other arm will be extended behind the shoulder. The assessment measures the distance between the finger tips of both hands.

- **When collected:** Baseline, final visit (~10 weeks)
- **Quality of life (QOL).** QOL changes will be captured using the Functional Assessment of Cancer Therapies (FACT) questionnaire including the Endometrial subscale (FACT-En).³² These measures will be repeated at the study mid-point (5 weeks) to assess changes over time.
 - **When collected:** Baseline, mid-point (~5 weeks), final visit (~10 weeks)
- **Mental well-being.** Changes in mental well-being (including anxiety, depression, and fatigue) will be assessed using standardized PROMIS measures.³³ These measures will be repeated at the study mid-point (5 weeks) to assess changes over time.

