9.3 Subject Population(s) for Analysis

The populations for this investigation include:

- All-randomized population: Any subject randomized into the study, regardless of whether they received study agent
- All-treated population: Any subject randomized into the study that received at least the instructional visit of the intervention
- Protocol-compliant population: Any subject who was randomized, was allocated to the exercise group and provided at least one set of data elements required by the protocol.

9.3.1 Describe the types of analysis:

- **Primary Analysis:** The primary objective includes measuring the percentage of completed sessions compared to prescribed, and a one-sample t-test will be conducted to determine if that proportion, across participants, is >90%. A one-sample t-test will be done to determine if retention is >90%.

- **Secondary Analyses:** The secondary analyses includes measuring the objective and functional changes from pre to post intervention as well as differences between groups. Paired ANOVAs and descriptive statistics will be used to analyze functional and objective data, as well as participant feedback data, including satisfaction with each component of the intervention.
- **Exploratory, longitudinal analyses:** Content analysis will be done on the qualitative interviews to examine barriers to physical activity, as well as satisfaction with the intervention, and identification of themes to improve the intervention. Although formal hypothesis testing is not part of our specific aims, we will conduct longitudinal analyses of the data we collect to estimate potential magnitude of expected changes, as well as longitudinal analysis of the repeated measures.
- **Safety Analysis:** The safety analysis includes simple descriptive analysis about the number of adverse events over the course of the intervention between groups and across sites.

9.4 Planned Interim Analysis:

There are no planned interim analyses for this investigation.

10 Data Collection, Handling and Record Keeping

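### The Appendix 1 form and the Section 8 arm text show mid-point questionnaires for the exercise arm only, in conflict with Section 8.1 and Table 3, which set no arm limit

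*Combined protocol and SAP*

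**What the plan says.** Four places in the combined protocol and SAP set the mid-point schedule, and a fifth uses the data.

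- **Appendix 1 (tracking form).** The blocks are labelled by arm. Baseline and final assessments are for all participants. The block between them is headed "Intervention Period (Intervention group", and it alone contains the rows "Mid-point (5 week) Questionnaires Sent (5" and "Actigraph mailed out". No wait-list assessment row falls between the baseline and final blocks.
- **Section 8, arm descriptions.** Under the exercise heading: "At the mid-point of the study, participants will receive an email with the questionnaires". The wait-list paragraph names the final-visit measures ("participants will complete the same study measures (body composition, functional fitness testing, blood sample collection, and anthropometrics") and adds: "Participants in the wait list group will also complete accelerometer (Actigraph) assessments at three study points". One of those three points is the 5-week mark. The paragraph does not mention questionnaires.
- **Section 8.1.** Quality of life, mental well-being and self-efficacy are each listed at baseline, about 5 weeks and about 10 weeks, with no arm named: "These measures will be repeated at the study mid-point (5 weeks) to assess changes over time".
- **Table 3.** Quality of life and self-efficacy are ticked at 4-6 weeks, and the columns are not split by arm.
- **Section 9.3.1.** The exploratory analyses include estimation of the likely size of changes "as well as longitudinal analysis of the repeated measures". The arms that enter this analysis are not stated.

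**The concern.** Appendix 1 is the working checklist. An assessment that has no row for a woman's arm is easily never sent, and a 5-week questionnaire that was not sent cannot be collected later. The arm descriptions in Section 8 would not alert staff to the gap, because they follow the same pattern as the form.

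If the mid-point questionnaires came from the exercise arm alone, changes from baseline to 5 weeks in quality of life, mental well-being and self-efficacy would be uncontrolled. They could not be separated from the passage of time or the effect of repeat testing. Aim 3 in Section 2.2 also judges tolerability partly by the share of women who complete every measure. That share is hard to define if it is unclear whether the mid-point set was due in half the sample.

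**Working it through.** The plan gives no figure to reproduce here, so the check sets the passages side by side.

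| Source | Mid-point questionnaires, wait-list arm | Mid-point accelerometer, wait-list arm |
|---|---|---|
| Section 8, wait-list paragraph | Not mentioned | Stated |
| Section 8, exercise text | Email sentence sits here and names no arm | Stated for the exercise arm |
| Section 8.1 | Scheduled, no arm limit (three instruments) | Scheduled, no arm limit |
| Table 3 | Ticked for quality of life and self-efficacy, arms not split | Ticked, arms not split |
| Appendix 1 | No row | No row |

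1. **Accelerometer.** Section 8 states that wait-list women wear it at 5 weeks, and Appendix 1 has no row for it. This is a direct contradiction, so the form needs correction whatever was intended for the questionnaires.

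2. **Questionnaires.** Section 8.1 read as it stands covers both arms, and the form covers one. Section 8.1 does name the arm when it means one: the extra five weeks of exercise logs are limited to the intervention arm. That favours reading its mid-point schedule as applying to everyone.

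3. **Weight of Table 3.** It adds less than it seems to. It also ticks device-measured activity, satisfaction and safety at 15 weeks without splitting the arms, although Section 8 says the wait-list arm has no five-week follow-up. An unsplit column in Table 3 does not prove that both arms are meant.

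4. **Size.** Section 9.1 gives 40 women, and Section 8.5 gives 1:1 blocked randomization, so the wait-list arm has 40 × 1/2 = 20.
   - Form and arm text followed literally: 0 of about 20 wait-list women have mid-point questionnaires. Up to 20 of 40 records are missing for each of the three outcomes.
   - Section 8.1 followed: up to about 20 wait-list women contribute, before any dropout.

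5. **What remains in the worst case.** Section 8.5 (baseline), Section 8.4.4 (final visit) and the all-participant blocks of Appendix 1 give both arms questionnaires at baseline and 10 weeks. The between-arm contrast over the full intervention can still be estimated, and so can within-arm change at 5 weeks in the exercise arm. Only the 5-week between-arm contrast for the questionnaires is lost.

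**The case against.** The strongest reply is that the plan nowhere excludes wait-list women from the mid-point questionnaires, and that the apparent exclusion comes from loose drafting. Four points support it.

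- The email sentence in Section 8 says only participants, and the next paragraph switches to naming the intervention group.
- The wait-list paragraph omits questionnaires even at the final visit, where those women plainly complete them, so its silence about the mid-point proves little.
- The form's headings are unreliable. A materials row marked for both groups sits in an intervention-group block. The qualitative interview sits under all participants, although Section 8 describes it for the intervention arm.
- The longitudinal analysis is exploratory, in a trial with a stated feasibility and descriptive focus, and it is not defined as a between-arm comparison.

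All of this stands, and it limits the point. A reader might infer that the plan leaves the wait-list arm with no data at all at 5 weeks, or that the questionnaires are absent there by design. The documents support neither reading. Wait-list women have 5-week accelerometry, and no passage states an exclusion for questionnaires. A reader might also infer that the longitudinal analysis as planned cannot be done. That does not follow either, because Section 9.3.1 does not say which arms it compares.

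The reply does not remove the practical risk. An unreliable checklist is still the one that staff sign, and for the accelerometer it contradicts Section 8 outright.

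**Conclusion.** This is a real inconsistency between the documents' own passages, in wording and on the form. It should be corrected, but it does not show a decision to leave the control arm unmeasured. The worst case is about 20 of 40 mid-point records missing for each of quality of life, mental well-being and self-efficacy, with no 5-week between-arm contrast for them.

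That size rests on three assumptions: full accrual of 40, equal allocation, and staff working from the form and the arm text rather than from Section 8.1. Primary adherence, retention and the baseline and 10-week comparisons are not touched. The point merits action because the loss could not be recovered and prevention costs almost nothing.

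**What to change.** - **Appendix 1.** Move the mid-point ActiGraph and questionnaire rows out of the intervention-group block into a new block headed *Mid-point assessments (all participants)*.
- **Section 8, wait-list paragraph.** Add the mid-point questionnaire email.
- **Section 9.3.1.** Say which arms enter the repeated-measures analysis. One sentence is enough.

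If mid-point questionnaires were meant for the exercise arm only, Section 8.1 and Table 3 should say so, and the 5-week questionnaire results should be described as uncontrolled. The accelerometer row of the form still has to be corrected in that case.

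The cost is a form and wording edit plus an emailed link to about 20 more women. The questionnaires are already completed online, so no extra visit is needed.
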